**Epidemiological and demographic data from 150 patients
diagnosed with covid-19 pneumonia in intensive care unit-
a retrospective, observational study in Istanbul, Turkey.**

06.06.2020

Study Protocol

Permission was obtained from Sisli Hamidiye Etfal Training and Research Hospital local Ethics Committee. The study was planned retrospectively, cross-sectionally and observationally with 193 patients hospitalized between 16 March 2020 and 15 May 2020 in five different covid-19 intensive care units in Sisli and Sariyer campuses of our hospital. While the covid-19 diagnosis of the patients was made by the Polymerase Chain Reaction (PCR) test, the disease was pre-diagnosed based on the criteria published by WHO on 12 January 2020 and the PCR results were concluded within 24 hours. Health workers, patients hospitalized less than 24 hours, patients with negative PCR tests, and patients who returned to intensive care unit after discharge were excluded from the study. The PCR samples were obtained from nasopharyngeal swab samples in non-intubated patients and endotracheal aspiration samples in intubated patients and examined in public health centers established in Ankara and Istanbul and then in the laboratories of our hospital respectively. The patients with intensive care requirements were admitted from emergency department and covid-19 wards to our units. The criteria for intensive care requirement was identified as $SpO_2 < 90\%$, $PaO_2 < 70$ mmHg, respiratory rate > 30 /min or $PaO_2/FiO_2 < 300$ despite conventional oxygen treatment of 5lt/min. Primary objective was the effect of defined data on 28-day mortality, and secondary objective was the impact of lymphocyte count, LDH, ferritin, D-dimer and procalcitonin levels, and SOFA score on prognosis, which are among the risk factors determined by previous studies. All data were evaluated and recorded using the standardized International Severe Acute Respiratory and Emerging Infection Consortium (ISARIC) case report forms, complemented by electronic records of the hospital, nurse observation records, and missing information was completed by telephone interviews with patients' relatives. Patients' age, gender, BMI, medical history, symptoms at admission (e.g., cough, fever, myalgia, gastrointestinal symptoms, headache),

concomitant diseases (e.g., diabetes mellitus, hypertension, chronic lung disease, cerebrovascular disease, kidney disease, heart disease, cancer, smoking) were recorded. The sequential organ failure assessment (SOFA) and acute physiology and chronic health evaluation score II (APACHE II) were worked out during their intensive care unit stays. Data from arterial blood gas and biochemistry laboratory test results on the first day and the days 7-14-21-28 of hospitalization; antiviral/antibiotic treatments and supportive treatments; all respiratory support methods and complications developed during hospitalization (e.g., acute coronary syndrome, acute renal failure) were recorded. Acute respiratory distress syndrome due to covid-19 infection was defined by 2012 Berlin criteria, acute coronary syndrome by > 99th percentile of troponin I concentration or the presence of dynamic changes in ECG, and the renal failure according to KDIGO criteria. The duration of pre-intensive care hospitalization, intensive care stay and the outcome (discharge or death) were recorded. Statistical data was expressed as standard deviation (SD) for continuously changing data and as percentile (%) for median and categorical variables. Wilcoxon rank-sum test or t-test were used based on parametric or non-parametric data for continuous variables to compare the differences between survivors and non-survivors. The survival rate was shown with the Kaplan-Meier estimator curve. Univariate and multivariate logistic regression models were used to investigate risk factors associated with death in intensive care.

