Statistical data was expressed as standard deviation (SD) for continuously changing data and as percentile (%) for median and categorical variables. Wilcoxon rank-sum test or t-test were used based on parametric or non-parametric data for continuous variables to compare the differences between survivors and non-survivors. The survival rate was shown with the Kaplan-Meier estimator curve. Univariate and multivariate logistic regression models were used to investigate risk factors associated with death in intensive care.

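### Two exclusions depend on events after ICU admission: patients who return to ICU are, read literally, dropped altogether, and the 24-hour minimum stay is not labelled as a landmark

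*Protocol*

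**What the plan says.** The protocol describes "193 patients hospitalized between 16 March 2020 and 15 May 2020 in five different covid-19 intensive care units". Besides health workers, it lists three excluded groups: "patients hospitalized less than 24 hours, patients with negative PCR tests, and patients who returned to intensive care unit after discharge were excluded".

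The objective is stated as "Primary objective was the effect of defined data on 28-day mortality". The predictors include "laboratory test results on the first day and the days 7-14-21-28 of hospitalization". On follow-up, the protocol says "The duration of pre-intensive care hospitalization, intensive care stay and the outcome (discharge or death) were recorded".

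The SAP, which repeats the protocol's statistical paragraph, adds "The survival rate was shown with the Kaplan-Meier estimator curve" and "Univariate and multivariate logistic regression models were used to investigate risk factors associated with death in intensive care".

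Neither document gives a time zero, a landmark, a rule for choosing among several ICU stays of one patient, a count of exclusions by reason, or a sensitivity analysis restoring excluded patients.

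**The concern.** Being a health worker is known at admission, and the protocol says PCR results were available within 24 hours. The other two exclusions can be applied only after watching what happens to the patient.

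- **Return to ICU.** Membership depends on leaving the ICU alive and coming back, possibly well inside the 28 days. The text excludes patients, not repeat stays.
- **Stay under 24 hours.** Every death in the first day is a 28-day death, yet it leaves the mortality figure, the Kaplan-Meier curve and the regression. So does every discharge in the first day.

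A reader would naturally take the result as 28-day mortality of PCR-positive ICU admissions. What is estimated is mortality in a group chosen partly by its later course. Associations between admission markers and death can shift as well, if the marker is related to early death, early discharge or readmission.

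**Working it through.** **1. What the rules condition on.** The documents give no figure to reproduce here, so the first check is of the text.

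- *Return rule.* Everyone it removes survived a first ICU stay; some will have died by day 28 and some not. A later starting point does not help, because at 24 hours nobody knows who will be discharged and readmitted. If the intention was only to avoid counting a patient twice, nobody is lost and the defect is one of wording, provided deaths up to day 28 after the first discharge are counted. The recorded outcome is discharge or death, so that needs saying.
- *24-hour rule.* The protocol uses the same verb for patients in the five ICUs, so ICU stay is the natural reading. Its separate mention of hospitalization before intensive care leaves some doubt. Either way the condition is met only after admission. If ICU stay is meant and the Kaplan-Meier clock starts at ICU admission, the first 24 hours of the curve contain no deaths by construction.

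**2. Mortality, illustration only.** All inputs are assumed except 150, which is the number in the protocol title; the protocol does not say it is the number left after exclusions.

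- Mortality among those analysed: p = 0.30, 0.45, 0.60
- Short stays removed: n = 3, 8, 15, of whom a fraction f = 0, 0.5 or 1 died
- Share of ICU survivors readmitted: r = 3%, 5%, 10%, of whom m = 0.5 died
- S = 150(1 − p) and R = rS/(1 − r), which gives R = 1.9 to 11.7 patients

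Shift in points on restoring both groups = 100 × [(150p + nf + Rm)/(150 + n + R) − p]. For one group alone, set the other's count to zero.

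| Restored | Shift (points) |
|---|---|
| Short stays, none died | −0.6 to −5.5 |
| Short stays, half died | −0.9 to +1.8 |
| Short stays, all died | +0.8 to +6.4 |
| Readmitted only | −0.4 to +1.4 |
| Both | −5.6 to +7.3 |

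The two extremes of the last row, both with r = 10%:

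- p = 0.60, n = 15, f = 0, R = 6.67: (90 + 0 + 3.33)/171.67 = 54.37%, so −5.63.
- p = 0.30, n = 15, f = 1, R = 11.67: (45 + 15 + 5.83)/176.67 = 37.26%, so +7.26.

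The second needs 15/(15 + 45) = 25% of first-stay deaths to fall in the first day. If that share is 10% and no short-stay patient survived, early deaths number 150p/9 = 5, 7.5 or 10, and the shifts are +2.3, +2.6 and +2.5 points.

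For scale, the 95% sampling half-width 1.96√[p(1 − p)/150] is 7.3, 8.0 and 7.8 points.

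**3. Odds ratio, illustration only.** This is a large-sample simulation with a standard normal marker x.

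- First-stay death: logit = −0.2 + ln(2)x.
- Deaths within 24 hours: 10% of first-stay deaths, related to x by an odds ratio of 0.5, 1, 1.5 or 2.
- Short-stay survivors: none, or 10% of first-stay survivors, related to x by 0.5 or 1.
- Readmissions: 5% or 10% of remaining survivors, related to x by 1, 1.5 or 2, half dying.

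Applying both exclusions changes the odds ratio by −0.18 to +0.30. The upper extreme (2.06 to 2.36) requires early death to be inversely related to the marker (odds ratio 0.5), with 10% readmitted and readmission related to it by 2. At n = 150 the standard error of the log odds ratio is 0.191, so the 95% interval around 2.0 is 1.38 to 2.91. The largest shift, ln(2.36/2.06) = 0.136, is 0.136/0.191 = 0.7 standard errors.

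**The case against.** The exclusions are stated openly, so nothing is concealed. The 24-hour rule fits the design: PCR positivity is required, results come within 24 hours, and first-day laboratory values are predictors. If the rule refers to the whole hospital stay, early ICU deaths among patients who came from the wards after a day or more in hospital remain in the cohort. The return rule may be loose wording for one record per patient. The primary objective concerns associations rather than a mortality proportion, and the illustrated effect on associations is modest.

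Most of this stands. It removes any case for insisting that short stays enter the main analysis; that is partly a choice of target population. It does not supply the missing time zero, landmark label or first-admission rule, and it does not rescue the return exclusion as written.

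Two stronger readings are tempting and unsupported:

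- A reader might infer that 193 − 150 = 43 patients (22.3%) were removed by these two rules. The documents do not say that 150 is what remains after exclusions. Even if it were, the 43 would also include PCR-negative patients and health workers.
- A reader might infer that mortality is understated or the odds ratios seriously biased. Dropping early deaths lowers mortality, dropping short-stay survivors raises it, and dropping readmitted patients can do either. No counts are given to settle the balance.

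**Conclusion.** The point holds as a defect in defining the cohort and labelling the result. Its firmest part is the return exclusion: followed as written, it selects patients on later events. On the milder reading it is a wording correction, and the text does not say which is meant. The 24-hour rule is acceptable as a landmark, but only if the result is named as one.

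Neither direction nor size can be established from the documents. Under the less extreme assumptions the mortality shift is about 1 to 3 points either way, inside the sampling half-width; reaching 5 to 7 points takes corner cases. Unlike sampling error, such a shift would not show in a confidence interval. The effect on odds ratios is probably modest. These figures rest wholly on assumed counts and are not bounds. The case for change is a correct denominator and label at small cost, not a demonstrated large bias.

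**What to change.** 1. Replace the return exclusion with: *Each patient is analysed once, from the first ICU admission, and followed to day 28 regardless of readmission; a repeat stay is not a separate record.*
2. State that the 24 hours refer to ICU stay, and choose one of two courses. Either keep the rule as a landmark, name the result *28-day mortality among patients in ICU at 24 h*, and count time from 24 hours in the Kaplan-Meier curve and the regression; or count time from first ICU admission with short stays included. In both cases say from which moment day 28 is counted.
3. Report the number and outcome of patients for each exclusion reason. As a sensitivity analysis, give mortality with PCR-positive stays under 24 hours restored, discharges as well as deaths.

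**Cost.** No new recruitment, but more than a change of wording. Stay durations and outcomes are recorded for study patients; nothing says that case report forms exist for excluded ones, so limited chart extraction is needed. Some short-stay patients will lack complete first-day data, which affects the regression but not the mortality count. Day-28 status must be traced for those discharged. The protocol says "missing information was completed by telephone interviews with" patients' relatives, so a contact route exists, though it is not described as tracing vital status in excluded patients.

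### Acute coronary syndrome is defined so that an isolated troponin I above the 99th percentile is sufficient, so myocardial injury of any cause is counted under a coronary label and its reported frequency is overstated.

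*Protocol*

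**What the plan says.** The sentence on definitions in the Protocol (section Study Protocol) gives "acute coronary syndrome by > 99th percentile of troponin I concentration or the presence of dynamic changes in ECG". The same sentence takes ARDS from the Berlin criteria and renal failure from KDIGO; the ACS rule cites no published criteria.

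The preceding sentence sets the role of the variable: "complications developed during hospitalization (e.g., acute coronary syndrome, acute renal failure) were recorded". It also covers "biochemistry laboratory test results on the first day and the days 7-14-21-28 of hospitalization"; troponin is not named there. Comorbidities include "cerebrovascular disease, kidney disease, heart disease, cancer, smoking) were recorded".

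On the link to outcome, the Protocol states "Primary objective was the effect of defined data on 28-day mortality", and the SAP states "Univariate and multivariate logistic regression models were used to investigate risk factors associated with death in intensive care". Neither document lists covariates. The SAP does not mention ACS or troponin and does not alter the definition.

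**The concern.** A troponin I above the 99th percentile shows that heart muscle has been injured. It does not show that the cause was coronary. Entry to these units rests on hypoxaemia or a raised respiratory rate despite oxygen, kidney and heart disease are recorded comorbidities, and acute renal failure is a recorded complication. Each offers a non-coronary or long-standing reason for a raised value, and none of them qualifies the definition.

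Two results are exposed. The first is the complication frequency: the count reported as ACS would include patients with myocardial injury from other causes. The second is conditional. If the variable is compared between survivors and non-survivors or entered in the logistic models, an association with death could be read as coronary events contributing to mortality when it reflects severity, renal failure or earlier disease.

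**Working it through.** **1. The rule as logic.** ACS = (troponin I above the 99th percentile) OR (dynamic ECG change). Either limb alone is sufficient. The word dynamic applies to the ECG only. For troponin, neither document asks for:
- a rise or fall, or a second sample;
- ischaemic symptoms, imaging or angiography;
- adjudication;
- comparison with an admission value;
- exclusion of another cause.

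The text does not say that one value is enough; this follows because nothing more is required. The ECG limb is also sufficient alone and can only add further labels.

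**2. The timing restriction.** Two statements have to be read together:
- "complications developed during hospitalization (e.g., acute coronary syndrome, acute renal failure) were recorded" shows an intention to count new events.
- "biochemistry laboratory test results on the first day and the days 7-14-21-28 of hospitalization" shows that first-day laboratory values are collected.

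Nothing connects them. There is no baseline value and no change rule by which an abstractor could tell an elevation present on arrival from one that developed later.

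**3. The link to death.** "Primary objective was the effect of defined data on 28-day mortality" does not say which data are meant. The secondary objective names lymphocyte count, LDH, ferritin, D-dimer, procalcitonin and SOFA; neither troponin nor ACS is among them. The logistic models have no covariate list, and no text excludes complications. Use of ACS as a predictor is therefore possible but not stated.

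**4. Size, as illustration only.** The documents give no troponin or ACS counts, so there is no plan figure to reproduce. Let t be the true ACS prevalence and q the share of the remaining patients with non-coronary or pre-existing troponin I above the limit. Assume that every true case is captured, and ignore false labels from the ECG limb. Then:
- labelled share = t + (1 − t)q
- share of labels that are true = t / [t + (1 − t)q]

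Assumed ranges are t = 2% to 10% and q = 10% to 40%. The denominator is ambiguous: the title has "Epidemiological and demographic data from 150 patients" and the text has "with 193 patients hospitalized between 16 March 2020 and 15 May 2020". Both are shown.

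| t | q | Labelled share | Labelled of 150 (true) | Labelled of 193 (true) | True share of labels |
|---|---|---|---|---|---|
| 2% | 10% | 0.02 + 0.98 × 0.10 = 11.8% | 17.7 (3.0) | 22.8 (3.9) | 0.02/0.118 = 17% |
| 2% | 40% | 0.02 + 0.98 × 0.40 = 41.2% | 61.8 (3.0) | 79.5 (3.9) | 0.02/0.412 = 5% |
| 10% | 10% | 0.10 + 0.90 × 0.10 = 19.0% | 28.5 (15.0) | 36.7 (19.3) | 0.10/0.190 = 53% |
| 10% | 40% | 0.10 + 0.90 × 0.40 = 46.0% | 69.0 (15.0) | 88.8 (19.3) | 0.10/0.460 = 22% |

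The last column does not depend on which denominator is right. Its width, 5% to 53%, shows how far the size depends on the assumptions.

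**5. How an association could arise without a coronary effect (also illustration).** Assume mortality of 40% without injury, 70% with non-coronary injury, and 40% in true ACS, so that coronary events add no risk at all. For t = q = 10%, mortality among labelled patients is (0.10 × 0.40 + 0.90 × 0.10 × 0.70)/0.19 = 54.2%. The odds ratio against unlabelled patients is (0.542/0.458)/(0.40/0.60) = 1.78. For t = 2% and q = 40% the same calculation gives 3.27. The label would appear to predict death although coronary events play no part.

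**The case against.** The strongest reply has four parts.

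- **Pre-existing elevation.** A reader might infer that a patient with a stable raised troponin on day 1 is counted as having developed ACS. The documents do not say so. Recording is limited to complications arising in hospital, and applying that limit would exclude a known prior elevation. This stands: what is missing is a way to apply the limit, not a rule that overrides it.
- **Link to death.** A reader might infer that ACS is a planned predictor of mortality. It is not named in either objective or in any model. This stands, so the concern about mortality must remain conditional. That the definition is openly stated helps a careful reader, but does not make the label accurate.
- **Size.** Any figure for the proportion of false labels rests on inputs from outside the documents. This stands in full.
- **Feasibility.** A reader might assume that the variable can simply be recoded from data in hand. No text says that serial troponin values, ECG tracings or ischaemic symptoms during the stay were abstracted. If troponin followed the laboratory schedule, values would be about a week apart, which suits an acute rise-or-fall criterion poorly. This also stands, and it rules out a fix that relies on such a criterion for every patient.

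It can also be said that ACS is one example complication in a retrospective descriptive study and that the 28-day mortality endpoint is untouched. That is correct and limits the importance of the point. It does not answer the central objection: the rule followed exactly puts isolated troponin elevation into a reported ACS count.

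**Conclusion.** The point holds in a limited form. As written, the definition measures myocardial injury of any cause or ECG change, and calls it ACS. The reported ACS frequency is therefore overstated. That direction follows from the or, given that some patients in this cohort have raised troponin I without a coronary event and that they are not outnumbered by true events meeting neither limb. The size is unknown; the 5% to 53% range above is illustrative and should not be cited as an estimate.

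The handling of elevations already present on the first day is a gap in the definition, not a stated error. Misreading of an association with death arises only if ACS is analysed against survival, which the documents neither plan by name nor exclude. The mortality endpoint itself is unaffected. The change is worth making because it alters a reported result at small cost.

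**What to change.** This is a research classification only and implies nothing about patient care.

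1. Report troponin-only cases as myocardial injury, not ACS.
2. Split them into raised at first measurement and new during the stay, and state the day of the first measurement. Only new cases enter the complication table.
3. Show ECG-only cases and cases meeting both limbs as separate categories.
4. Reserve the ACS label for cases where the records support more than an isolated troponin value, and state what that support was.
5. If troponin-only status is related to death, report the association as one with myocardial injury.

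**Cost.** Fewer events will carry the ACS label. Some chart re-review is needed, because the documents do not say that serial troponin or ECG data were abstracted. Patients with only one troponin value cannot be classed beyond injury. If re-review is not possible, relabelling the troponin-only group still removes the misleading label at almost no cost.

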Statistical data was expressed as standard deviation (SD) for continuously changing data and as percentile (%) for median and categorical variables. Wilcoxon rank-sum test or t-test were used based on parametric or non-parametric data for continuous variables to compare the differences between survivors and non-survivors. The survival rate was shown with the Kaplan-Meier estimator curve. Univariate and multivariate logistic regression models were used to investigate risk factors associated with death in intensive care.

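### The primary objective is 28-day mortality, but the only regression models ICU death with no time limit, so no planned model estimates effects on the primary outcome.

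*SAP*

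**What the plan says.** The objectives sentence under the Study Protocol heading reads: "Primary objective was the effect of defined data on 28-day mortality". It gives a horizon but no day 0, and it does not restrict where the death occurs.

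The statistical paragraph is the whole of the SAP and is repeated at the end of the Protocol. It lists three analyses of outcome:

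- Regression: "Univariate and multivariate logistic regression models were used to investigate risk factors associated with death in intensive care". No time limit is given.
- Wilcoxon rank-sum or t-tests on continuous variables, used "to compare the differences between survivors and non-survivors". No time point or place is attached to survival.
- "The survival rate was shown with the Kaplan-Meier estimator curve". No origin, horizon, grouping or censoring rule is given.

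On the outcome data, the Protocol says: "The duration of pre-intensive care hospitalization, intensive care stay and the outcome (discharge or death) were recorded". It does not say whether discharge is from the ICU or from hospital, and it does not list vital status at day 28 as a variable. Day 28 appears once more, for blood gas and biochemistry results, which are taken "on the first day and the days 7-14-21-28 of hospitalization".

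**The concern.** An objective about effects on 28-day mortality needs an analysis that relates factors to death by day 28. The only model relates them to dying in the ICU at any time. No sentence says that the two are the same, so two analysts could follow this text and build different outcome columns.

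Odds ratios for ICU death would then be reported against a 28-day objective. If a factor also affects how long patients stay in the ICU, the patients classified differently need not be spread evenly over its levels, and its odds ratio can shift in either direction.

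**Working it through.** **1. The two outcomes side by side.** The plan states no figure to reproduce on this point, so the first check is on definitions.

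| Patient | 28-day mortality (objective) | ICU death (model) |
|---|---|---|
| Dies in ICU by day 28 | event | event |
| Dies in ICU after day 28 | no event | event |
| Dies by day 28 after leaving ICU | event | no event |
| None of these | no event | no event |

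The definitions agree only if the two middle rows are empty.

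**2. Do the other analyses fill the gap?** The Kaplan-Meier curve could be read at day 28, but it estimates no factor's effect. The survivor comparison is unadjusted, is specified for continuous variables, and has no time point. Neither gives an adjusted effect on 28-day mortality.

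**3. Late ICU deaths (second row).** The documents give no mortality or length of stay, so these are assumptions: ICU mortality p of 30-60%; median ICU stay m of 7-14 days, the same for deaths and survivors; constant hazard h = ln 2 / m; uniform admission over 16 March to 15 May 2020 (61 days inclusive).

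With unlimited follow-up, late deaths = p × exp(−28h):

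- p 0.30, m 7: 0.30 × 0.0625 = 1.9 points
- p 0.45, m 10: 0.45 × 0.1436 = 6.5 points
- p 0.60, m 14: 0.60 × 0.25 = 15.0 points

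If follow-up ended on the protocol date, 6 June 2020, each patient has F days, from 22 (admitted 15 May) to 82 (admitted 16 March). Late deaths = p × the mean over the 61 days of [exp(−28h) − exp(−Fh)], taken as 0 when F ≤ 28:

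- p 0.30, m 7: 1.37 points, 2.0 of 150
- p 0.45, m 10: 4.28 points, 6.4 of 150
- p 0.60, m 14: 8.77 points, 13.2 of 150

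**4. Adding the third row.** A separate illustration assumes 28-day mortality of 40-60%, 0-15% of ICU deaths after day 28, and 0-10% of 28-day deaths outside the ICU. The number classified differently then runs from 0 to about 23 of 150. The upper end is 90 deaths by day 28, of which 9 are outside the ICU and 81 inside; late ICU deaths are 81/0.85 − 81 = 14.3; total 23.3, or 15.5%.

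**5. Effect on an odds ratio.** Take a factor present in half the patients, with 28-day mortality of 30% v 50%: OR = (0.50/0.50)/(0.30/0.70) = 2.33. Add the middle case of 4.28 points of late deaths overall:

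| Late deaths fall | Risks | OR |
|---|---|---|
| Equally on both groups | 0.3428 v 0.5428 | 2.28 |
| All in the lower-risk group (+0.0856) | 0.3856 v 0.50 | 1.59 |
| All in the higher-risk group (+0.0856) | 0.30 v 0.5856 | 3.30 |

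The last two rows are outer bounds for the middle case only. At 8.77 points the same arithmetic gives 2.25 for an even split, with bounds of 1.10 and 4.86.

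**6. Follow-up dates (supporting only).** Patients were "hospitalized between 16 March 2020 and 15 May 2020". An ICU admission on 15 May reaches day 28 on 12 June, six days after the protocol date. Admissions from 10 to 15 May, 6 of 61 days (9.8%), had under 28 days by then. No data cut-off is stated, so this shows what needs confirming, not an error.

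**The case against.** The strongest reply is that the regression sentence is loose wording. The plan is one short paragraph about an ICU cohort, 28 days is the only mortality horizon in it, and laboratory data run to day 28, so ICU death could be shorthand for 28-day death. That may be so, but the text does not say it, and this sentence defines the dependent variable of the only model.

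The regression might instead serve the secondary objective on prognosis, which has no horizon. That would leave the primary objective with no model at all.

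The primary objective does not ask for adjustment, so the survivor comparison could serve it. This holds only if survival is taken at day 28, which is not stated, and even then the result is unadjusted.

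Three points stand as limits on size:

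- Excluding patients who returned to the ICU may reduce deaths by day 28 after ICU discharge. It does nothing about late ICU deaths.
- All the magnitudes rest on assumed rates, and nothing in the documents supports putting every late death in one group. With an even split the change is negligible.
- The laboratory days may be counted from ICU admission, since the Protocol also speaks of being hospitalized in the ICUs. The count is ambiguous and, either way, does not define the outcome.

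**Conclusion.** The concern holds. The plan's only model has an outcome that differs from the one in its primary objective, and nothing in either document equates them. This rests on the wording alone and does not depend on the assumed rates.

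The practical size is unknown. It is zero if every death occurred in the ICU by day 28. Under the assumptions in the working, a handful of patients could be misclassified (about 6 late ICU deaths of 150 in the middle case), which matters for an odds ratio only if they cluster in one level of the factor. Because it concerns the primary objective and is cheap to remove, it should be corrected before results are reported.

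**What to change.** - Make the dependent variable of the logistic models all-cause death within 28 days of one stated origin, for example ICU admission, whether or not the patient has left the ICU.
- Use the same definition for the survivor and non-survivor groups, and the same origin for the Kaplan-Meier curve.
- State whether discharge means from the ICU or from hospital.
- For patients discharged before day 28, obtain day-28 status from hospital records and the route the Protocol already uses: "missing information was completed by telephone interviews with patients' relatives". Count and report any who remain unknown.
- Confirm that every included patient has 28 days of follow-up at data close (12 June 2020 for an ICU admission on 15 May).
- Report ICU death as a separately labelled secondary outcome.

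The cost is a few sentences in the SAP and a short vital-status check, using sources already in the Protocol. If 28-day death was always what was coded, only the wording needs to change.
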